12.0 Data Management

The research material obtained from human participants in this protocol will include:

1. De-identified survey questionnaire to obtain normative attitudes and behavior related to alcohol use and sexual assault;
2. De-identified survey and open ended questions assessing the usability of the interventions within an open pilot trial;
3. De-identified survey and open ended questions assessing the usability of the interventions within a randomized pilot trial and follow-up alcohol use and sexual assault-related constructs 3 months after receipt of intervention (if assigned to ASAP condition) or completion of baseline survey (if in control condition).

Recruitment Sources/Sites Where Data Will Be Collected and How These Data Will Be Obtained, Managed, and Protected:

All quantitative data will be collected via mHealth application or online (via DatStat Illume) – on a secure server hosted at Brown University (the site of study Co-Investigator, [name]). Surveys will be identified only by a unique numeric ID, that will be different from the participant ID. A separate list will link participant name to participant ID (i.e., the database), and a separate file will link the survey ID to the participant ID that will only be available to the PI and GSU study staff. Thus, identifying information will not be stored with participant data or on the Brown University server. Records containing potentially-identifying information (i.e., consent forms and master list linking participant ID to survey ID, database of participant names and contact information) will be kept separate from research data. All information will be treated as confidential material and will be available only to research staff. All paper records will be kept in locked file cabinets. No participant will be identified in any report of the project. Computer data files will be password protected. Computer data files will be available only to authorized personnel and no names or obvious identifying information will be stored in data files. Data transmissions to and from the data server are encrypted by SSL (Secure Socket Layer) and 40, 56, or 128-bit Public Key Encryption technology. A VeriSign security certificate has been obtained to verify SSL encryption. Data will be downloaded to password-protected computers belonging to research staff or investigators. Databases on the server are password protected and can be accessed only by project staff that has completed requirements and training in Human Subjects Protections. The Illume DatSTAT survey is also administered via a “https:” site, which provides enhanced security over a “http:” site. Participants IP addresses will not be collected in cases where online screening surveys are completed outside of the laboratory space.

13.0 Provisions to Monitor the Data to Ensure the Safety of Subjects (if applicable)

A data and safety monitoring plan approved by the sponsor (NIAAA) will be submitted as an amendment.

14.0 Withdrawal of Subjects (if applicable)

Participants are allowed to withdraw from the study at any time. They will be asked to either email or call the study to inform us that they are no longer interested in participating in the study and we will either remove their data from the study or no longer contact them to participate in the study based on their request.

15.0 Risks to Subjects

This study has minimal risk to subjects.

Potential risks include possible embarrassment or discomfort related to sensitivity of the information disclosed on the questionnaires. Research has found that the assessment of details of a traumatic event (e.g. sexual assault) has in general left participants feeling like they have gained something positive from the experience (Dyregrov et al., 2000; Griffin et al., 2003; Johnson & Benight, 2003; Walker et al., 1997). This research has shown that although a small number of participants do report some distress after assessment, they express willingness to participate again in the future. In addition, research at the University of Washington examining sexual assault risk perception and resistance (1R01AA12219; PI: [name]; “Alcohol and Acquaintance Sexual Assault Risk Perception”), participants were contacted approximately 3 weeks after participation to inquire

about negative effects of participation. No participant reported any negative effects, nor did any request follow-up contact with project staff or outside referral. Rather, several participants expressed appreciation that the topic was being studied, and two participants refused payment because they "just wanted to help other women." Thus, we feel that participation in the proposed research will not cause extreme psychological distress. Relevant safeguards for protection against potential risks are detailed below in the next question.

Breach of confidentiality is also a risk, however, we are taking precautions to ensure that this risk is minimal. Similarly, if a participant is threatening to hurt her/himself or someone else, confidentiality may have to be broken to make a report to the necessary authorities. Given that suicidality is a risk of sexual assault victimization, while not a direct risk of the study, it is an important issue to assess and monitor closely with participants. Procedures for assessing and addressing suicide attempts are addressed in the following protection against risks section.

With regard to potential alternative treatments, all college students will receive some form of sexual assault prevention programming at college as a standard care. Therefore, those who participate in the study will only receive additional services on top of standard care and in no way will participating in the current study take away their standard of care. When the study is advertised to potential participants, it will be made very clear that students have the right to choose not to participate in the study and to be provided with appropriate referrals if they so prefer, including resources at the college regarding alcohol and sexual assault.

Protection Against Risk: To protect against violations of confidentiality: (a) a federal certificate of confidentiality is included in all NIH studies, which renders the data immune from subpoena (due to the sensitivity of some of the data that we are collecting - e.g., self-reports of alcohol use and sexual assault - and the potential legal jeopardy faced by some of the participants); while aware of the ambiguities about the reach of the certificates, we are convinced that they are the best protection available for confidentiality of research data; (b) all staff will sign confidentiality agreements, and our training sessions will emphasize the critical importance of confidentiality; and (c) computers containing the data will be password-protected as a security precaution to eliminate unauthorized access.

To minimize distress or discomfort associated with participation in the study (from either assessment or the intervention): (a) participants will be informed that they can discontinue participation at any time; and (b) if other problems arise, a licensed psychologist will be available to address the distress. Upon completing the survey, they will be given local resources regarding alcohol use, sexual assault, and mental health resources (see Resources). All participants will be given this information, regardless of their risk. Participants will be given the option of contacting the study staff if they are distressed by the study procedures. Members of the research team are licensed clinical psychologists and are well-equipped to follow-up with individuals in need. As been the case with our previous studies, we will establish a schedule in which members of the research team will be on call 24 hours a day, seven days a week to address urgent matters. If a participant is distressed and wishes to talk with a member of the research team, the clinical psychologist team member will be available at all times during the study period.

A detailed safety plan - detailing what to do and whom to speak with if ideation should occur - will be included in standard referral information provided to all participants, including specifics on how to access 24-hour care for suicidality via dialing 9-1-1 and/or going to the closest emergency department when a PI is not available. Thus, a 24-hour safety plan is in place, including access to medical care 24 hours per day. Further, any participant in which it is deemed that medication is warranted will be referred to a psychiatrist for such services and monitoring. Suicidal risk factors - including suicidal ideation, intent, plan, and means - will continue to be assessed on an ongoing basis throughout the students' participation

in the study for those who are participating in the open and randomized pilot trial.

To address electronic data security, [name] will work closely with the programmers at Brown University, to support electronic data security. Questionnaire data will be collected via DatStat Illume survey software, which is maintained by programmers at Brown University – the site of Co-Investigator [name]. These programmers have extensive experience safeguarding the security and integrity of sensitive materials, including protected health information and sensitive financial information. Data transmissions to and from the data server are encrypted by SSL (Secure Socket Layer) and 40, 56, or 128-bit Public Key Encryption technology. A VeriSign security certificate has been obtained to verify SSL encryption. Data will be downloaded to password-protected computers belonging to research staff or investigators. Databases on the server are password protected and can be accessed only by project staff that has completed requirements and training in Human Subjects Protections. The Illume DatSTAT survey is also administered via a “https:” site, which provides enhanced security over a “http:” site. Participants IP addresses will not be collected in cases where online screening surveys are completed outside of the laboratory space. Respondent confidentiality will be masked in all data files by the use of project identification numbers rather than personal information. All other electronic records, including digital recordings of interview feedback, are de-identified in collection and will be maintained in password-protected locations on the secure server. The only document linking participants with identification numbers will be retained in an encrypted file on the secure server with access limited to the investigative team. Data presented at professional meetings or published in journals or books will not allow identification of individual participants. These procedures are expected to minimize any potential adverse effects from participating in this study.

16.0 Potential Benefits to Subjects or Others

The risks to college students participating in this project are minimal and do not exceed risks associated with participating in mandatory sexual assault prevention programming while in college. Potential benefits to participants who receive the prevention program are substantial, including decreased likelihood of alcohol misuse and sexual assault, thereby decreasing the risk of subsequent development of substance use disorders and sexual (re-)victimization/(re-)perpetration, though these cannot be guaranteed. In addition, the successful demonstration of an intervention for alcohol use and sexual assault would be of significant benefit to society. Further, this technology could be adapted to other populations and university settings if effective.

Importance of the knowledge to be gained: Sexual assault is widespread on college campuses and individuals who engage in heavy episodic drinking are more likely to experience sexual assault victimization, to perpetrate sexual assault, and to not intervene when witnessing a potential sexually assaultive situation. mHealth interventions are promising and have the potential to reach a large targeted group of college students who use alcohol. The proposed research is a first step of establishing the research team, programming, feasibility, and preliminary efficacy of the research protocol. If promising, this study will lay the groundwork for a large-scale R01 application to test the efficacy of tailored gender-specific ASAP in a randomized controlled trial. The minimal risks to participants are reasonable given the importance of the knowledge to be gained.

17.0 Sharing of Results with Subjects

Results will not be shared with participants.

PROTOCOL TITLE:

Alcohol and Violence Prevention for College Students

PRINCIPAL INVESTIGATOR:

[name]

Sample Size and Analyses

Sample size for the randomized pilot trial was determined, using PASS©, to estimate the variability within a reasonable margin of error. This calculation also accounted for the low base rates of SA and 20% attrition. To estimate variability using a 95% two-sided confidence interval, within a margin of error of 80%, 53 total participants are needed. (For example, if the standard deviation is 10, the confidence limits would be 7 to 15. To design a future trial if we wanted to be conservative, we will use a standard deviation of 15.) We further adjusted the sample size considering low base rate and attrition. SA victimization is a low base-rate experience with a total of 60% of college women who engaged in HED reporting at least one SA victimization experience within a 3-month follow-up period¹². To account for this low base-rate experience, a total of 132 participants are needed. Preliminary studies by the research team estimate that there will be 20% attrition over a 3-month follow-up period, therefore, the final sample size for this pilot study will be 162 (n = 54 per risk group) to account for attrition rates.

We will perform secondary analyses using linear mixed model ANOVAs to determine the factors that potentially predict outcomes including alcohol use, SA victimization, and bystander intervention.

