1.0 Objectives / Specific Aims

Aim 1: Modify Alcohol and Sexual Assault Prevention (ASAP) content to an eHealth format to include personalized content for each risk group (1. cisgender heterosexual men; 2. cisgender heterosexual women; and 3. sexual and gender minorities).

Aim 1a: Assess normative behaviors ($n = 750$) regarding alcohol use and SA for feedback from Arizona State University (already completed and de-identified data being analyzed) and Georgia State University.

Aim 1b: Adapt and assess initial acceptability of a workbook version of the intervention content among key stakeholders (college administrators and students from each risk group [$n=5$ from each group]) from Arizona State University (already completed and de-identified data being analyzed) and Georgia State University.

Aim 2: Open Pilot Trial. Obtain usability of ASAP among 30 students who engage in HED (10 from each risk group) in an open pilot trial at Arizona State University (already completed and de-identified data being analyzed) and Georgia State University.

Aim 3: A pilot to assess effect size and variability for planning a randomized trial in the future. This Aim will only be conducted at Arizona State University. Randomize students who engage in HED to ASAP or control condition to observe preliminary effect sizes and estimate the variability using a 3-month follow-up. Sample size was determined to estimate the variability within a reasonable margin of error. This calculation also accounted the low base rates of SA and 20% attrition. This led to a sample size of 162 students ($n=54$ from each risk group).

By accomplishing these aims, we will have established the research team, programming, feasibility and preliminary efficacy of the research protocol. If promising, this study will lay the groundwork for an R01 application to test the efficacy of ASAP.

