5.0 Inclusion and Exclusion Criteria/ Study Population

College students aged 18-25 will be recruited from Arizona State University (no participants will be recruited until an inter-institutional agreement is signed by Arizona State University, submitted as an amendment to the MUSC IRB and approved by the MUSC IRB) to complete questionnaires regarding their attitudes and behaviors related to alcohol use, sexual assault victimization, sexual assault perpetration, and bystander intervention. Human subjects are also being recruited to participate in an open pilot and a randomized pilot to determine usability as well as estimate effect size for a larger grant. In Aim 1a, we will recruit 750 college students aged 18-25 (n= 250 women; n=250 men; n=250 sexual/gender minorities) from both Arizona State University (data already collected and have de-identified dataset) and Georgia State University. In this aim, human subjects are needed to assess setting-specific normative attitudes and behavior for alcohol use and sexual assault to incorporate into the intervention content. Aim 1b includes alpha testing of a workbook version of the intervention, which will include interviews with key stakeholders (college administrators and 15 students) to inform programming content at both Arizona State University (data already collected and have de-identified dataset) and Georgia State University. In Aim 2, we will recruit 30 students (10 from each risk group (cisgender heterosexual men, cisgender heterosexual women, and sexual/gender minorities) who engage in heavy episodic drinking in the past month to participate in an open pilot trial to obtain usability feedback to integrate into the intervention content. In Aim 3, which will only be collected from Arizona State University, we will recruit 54 students who engage in heavy episodic drinking in the past month from each risk group (cisgender heterosexual men, cisgender heterosexual women, and sexual/gender minorities) for a total of 162 students aged 18-25 to participate in a randomized pilot trial. Aim 3 focuses on observing effect sizes and estimating the variability using a 3-month follow-up design to design a larger study for an R01 application. In this IRB application at Georgia State University, a total of 967 participants will be recruited (Aim 1a = 750 students from GSU, Aim 1b = 25 [25 students and 10 administrators] from GSU, Aim 2 = 30 students from GSU, Aim 3 = 162 students from ASU).

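### The SAP's precision statement does not reproduce: 53 participants and an SD of 10 give 95% limits of 8.4 to 12.4 (full width about 40%), not 7 to 15 and not 80%

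*SAP*

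**What the plan says.** The SAP (Sample Size and Analyses) sets the first step of the Aim 3 calculation as a precision target. The interval is specified by "To estimate variability using a 95% two-sided confidence interval", and the requirement is stated as "within a margin of error of 80%, 53 total participants are needed". The worked example is "if the standard deviation is 10, the confidence limits would be 7 to 15", followed by "To design a future trial if we wanted to be conservative, we will use a standard deviation of 15". The SAP then adjusts the 53 for the base rate of sexual assault (to 132) and for 20% attrition (to 162, or 54 per risk group).

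The Protocol relies on the same argument. Section 1.0, Aim 3, says "Sample size was determined to estimate the variability within a reasonable margin of error". Section 5.0 gives the purpose of Aim 3 as "observing effect sizes and estimating the variability using a 3-month follow-up design to design a larger study for an R01 application".

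**The concern.** The SAP names the quantity (a standard deviation), the confidence level (95%, two-sided) and the sample size (53 in total), so its limits can be checked directly. Limits of 7 to 15 around an SD of 10 are much wider than 53 observations should give.

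Two things depend on this. Precision of variability is the documents' stated basis for the size of Aim 3, and as written a reader cannot tell what precision 53 was meant to deliver, on which scale, or for which group. The upper limit of the example is also carried forward as a planning SD. Sample size for a comparison of means grows with the square of the SD, so a wrong upper limit would pass directly into the size of the next trial.

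**Working it through.** **Inputs (all from the SAP).** Two-sided 95% interval; n = 53 in total; example SD s = 10; stated limits 7 to 15; stated margin 80%; planning SD 15. The SAP does not say whether the 80% is a full or a half width, or whether it applies to the SD or the variance.

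**1. The SAP's example as written.** For normal data the limits for an SD are s × √(df/χ²), with df = n − 1. At df = 52 the 97.5% and 2.5% chi-square points are 73.81 and 33.97.

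- Lower: 10 × √(52/73.81) = 8.39
- Upper: 10 × √(52/33.97) = 12.37
- Full width: 3.98, or 39.8% of the SD (half-width about 20%)

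The stated 7 to 15 is not reproduced. A large-sample interval gives nearly the same answer: 10 ± 1.96 × 10/√104 = 8.08 to 11.92, width 38.4%. Using 51 or 53 degrees of freedom moves the limits by less than 0.04. Confidence of 90% gives 8.63 to 11.95, and 99% gives 7.96 to 13.28.

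**2. Does any definition of 80% return 53?** Smallest n that meets each definition:

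| Definition of 80% | SD scale | Variance scale |
|---|---|---|
| Full width | 17 | 57 |
| Distance to upper limit | 11 | 31 |
| Half-width | 7 | 20 |

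None gives 53. However, 53 is exactly the smallest n for which the full width on the SD scale is 40% or less.

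**3. Where could 7 to 15 come from?**

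| Reading | Limits around 10 | Full width | Conflict with the SAP |
|---|---|---|---|
| Variance of 10, n = 53 | 7.05 to 15.31 | 82.6% | The text says SD |
| SD, 17 per risk group | 7.45 to 15.22 | 77.7% | The text says 53 in total; 3 × 17 = 51 |
| SD, one arm of 26 | 7.84 to 13.80 | 59.6% | Limits and width |
| SD, one arm of 27 | 7.88 to 13.70 | 58.3% | Limits and width |

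The variance reading is the closest: its limits round to 7 and 15, and 15 − 7 = 8 is 80% of 10. On that reading, though, the 15 is a variance, and the matching SD is √15 ≈ 3.9.

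**4. Effect on the next trial.** The ratio of its size planned at SD 15 to its size planned at the correct upper limit U (observed SD 10) is (15/U)².

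| n behind the limit | U | Ratio |
|---|---|---|
| 17 per risk group | 15.22 | 0.97 |
| 43 (retained per risk group: 54 × 0.8 = 43.2) | 12.71 | 1.39 |
| 53 | 12.37 | 1.47 |
| 130 (retained, pooled: 162 × 0.8 = 129.6) | 11.39 | 1.73 |

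**The case against.** The strongest reply is that this is a one-word slip. Replace standard deviation by variance in the example, and 53, 7 to 15 and 80% all agree to the rounding used, so 53 need not be wrong. This is probably what happened, and the sponsor should check it first. It does not rescue the text: the SD label appears twice, the second time on the planning value, and a strict 80% full width for a variance needs 57.

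Second, a margin of error usually means a half-width, so describing 40% as half of the stated 80% assumes the full-width reading. That is correct. On the half-width reading the gap is larger, about 20% against 80%.

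Third, the SD of 10 is only illustrative, and the intended rule is evidently to plan from an upper confidence limit, which is sound. This also stands. The inflation is conditional, and there is none if 17 per risk group was meant.

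Fourth, about 130 retained participants would give limits of 8.9 to 11.4, tighter than the SAP promises, so the pilot loses nothing. That limits the seriousness of the error. It does not make the stated precision correct.

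**Conclusion.** The concern holds. As written, 53 participants, an SD of 10 and limits of 7 to 15 cannot all be right, and the 80% does not lead to 53 under any definition tested. The correct 95% limits are 8.4 to 12.4, with a full width of about 40% of the SD. The likely cause is variance limits presented as SD limits, but the SAP does not document their source, so this remains an inference.

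If the SD of 15 were reused with 53 taken as written, the next trial would be about 47% too large. The factor runs from 0.97 to 1.73 according to which n the limit describes. This pilot's enrolment, randomisation and analysis are unaffected: 53 can stand as the size for a 40% full width on the SD scale.

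The limits assume normally distributed outcomes. If alcohol use, bystander behaviour or victimisation scores are skewed, the chi-square interval could overstate the precision.

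**What to change.** 1. Check the PASS output for the scale (SD or variance), the width definition and the n that were entered.
2. Replace the example with: *With 53 participants, and assuming normally distributed data, the 95% confidence interval for an SD of 10 is 8.4 to 12.4 (full width about 40% of the SD).* If the output shows that a variance was meant, label the example as a variance and do not carry 15 forward as an SD.
3. Delete the 80%, or state its scale, whether it is a full or half width, and the n it applies to.
4. Replace the fixed planning SD of 15 with the upper 95% confidence limit of the observed SD, computed at the retained n. For an observed SD of 10 this is 12.4 at n = 53, or 11.4 at n = 130 if groups are pooled.
5. If precision within each risk group is intended, say so and give the limits at the retained size per group (8.2 to 12.7 at n = 43).

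The cost is a change to SAP wording. Enrolment and analysis stay as they are.

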4.0 Study Endpoints

Outcome variables include alcohol use, bystander behavior, and sexual assault victimization 3-months after the intervention. Further, self-blame will be assessed directly after receiving the intervention to ensure that the intervention does not have iatrogenic effects (even though previous iterations of this intervention have found no iatrogenic effects).

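### The SAP would plan the future trial on the upper limit of a normal-theory interval whose example limits fit a variance, not an SD; correctly computed, that limit is not conservative for skewed counts and has no use for a yes/no assault outcome

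*SAP*

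**What the plan says.** The SAP (Sample Size and Analyses) sets the precision target: "To estimate variability using a 95% two-sided confidence interval, within a margin of error of 80%, 53 total participants are needed". It illustrates the target in parentheses: "if the standard deviation is 10, the confidence limits would be 7 to 15". It then says how the estimate would be carried forward: "To design a future trial if we wanted to be conservative, we will use a standard deviation of 15". It names no outcome, scale or distribution for this calculation.

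The number is next raised for SA. The rate given is "60% of college women who engaged in HED reporting at least one SA victimization experience within a 3-month follow-up period", and then: "To account for this low base-rate experience, a total of 132 participants are needed". With 20% attrition the total becomes 162, or 54 per risk group.

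The endpoints are in Protocol section 4.0: "Outcome variables include alcohol use, bystander behavior, and sexual assault victimization 3-months after the intervention". No instrument or scoring is given. Protocol section 3.0, describing the team's earlier trial in college women, refers to SA severity and to frequency of incapacitated rape, so SA need not be scored yes/no.

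**The concern.** Variability is the quantity that Aim 3 was sized to deliver, and the SAP's cautious option is to plan the next trial on its upper confidence limit. Three things make that limit doubtful.

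- The example limits do not look like SD limits at n=53.
- The chi-square interval is exact only for normal data. Drinking and bystander measures are often right-skewed counts, and for such data the interval is too narrow.
- The only planning figure for SA is the share of women "reporting at least one SA victimization experience within a 3-month follow-up period". For a yes/no outcome the rate determines the SD, so there is no separate SD to bound.

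At stake is a future trial described as conservatively sized when the limit behind it does not give the protection implied.

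**Working it through.** **Inputs.** From the SAP: 95% two-sided interval, 80% margin, n=53, example SD 10 with limits 7 to 15, SA rate 60%, 162 randomised, 20% attrition. Completers: 162 × 0.8 = 129.6, about 130. With equal allocation (assumed; no ratio is stated) that is about 65 per arm and 54 × 0.8 / 2 = 21.6, about 22, per arm and risk group.

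**1. Reproducing 53 and 7 to 15.** The example has total width 8, which is 80% of 10, so the margin reads as total width relative to the estimate. The chi-square limits for a variance, as multiples of the estimate, are (n−1)/χ²(0.975) and (n−1)/χ²(0.025); for an SD, take square roots.

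- Shortest 95% variance interval with width at most 0.80: n=53 (width 0.799; at n=52 it is 0.808). Limits 0.666 and 1.465, so 10 becomes 6.7 to 14.7, which rounds to 7 and 15.
- Equal-tailed variance interval at n=53: 52/73.81 = 0.705 and 52/33.97 = 1.531, so 7.0 to 15.3. The width slightly exceeds 0.80, and meeting that target needs n=57.
- Equal-tailed SD interval at n=53: √0.705 = 0.839 and √1.531 = 1.237, so **8.4 to 12.4**. A width target of 0.40 also gives n=53, but not the limits 7 to 15.
- SD interval with width at most 0.80: only n=17.

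The SAP's number and limits therefore agree with each other only as a variance interval. At n=130 the SD factors are 0.891 and 1.139, so an SD of 10 gives 8.9 to 11.4.

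**2. What the label does to a future sample size.** Illustration (assumed difference of 5, two-sided 5%, 80% power): n per arm = 2(1.96+0.84)²SD²/5², giving 63 at SD 10, 97 at SD 12.4 and 142 at SD 15. Taken literally, 15 makes the next trial larger, not smaller.

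**3. Skewed counts (assumption).** Negative binomial outcomes with dispersion k, n=130, 40,000 simulated pilots per row:

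| Mean, SD (k) | Chi-square SD interval: coverage | True SD above its upper limit | True SD above 1.5 × sample SD | Bonett: coverage | True SD above Bonett limit |
|---|---|---|---|---|---|
| 10, 7.75 (2.0) | 79% | 11% | <0.1% | 93% | 6% |
| 10, 10 (1.1) | 70% | 16% | 0.03% | 92% | 7% |
| 2, 3 (0.57) | 58% | 24% | 0.6% | 91% | 8% |

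The nominal figure for the upper limit is 2.5%. Under heavier skew (mean 1; k=0.3 and 0.1) the chi-square limit is exceeded in 32% and 46%, and 1.5 × SD in 3.2% and 17%. At n=53 the three tabled cases give 10%, 16% and 24% for the chi-square limit, and 0.5%, 2% and 6% for 1.5 × SD.

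**4. SA scored any versus none.** SD = √(p(1−p)), with maximum 0.50 at p=0.5. At p=0.6, SD = √0.24 = 0.490.

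- Chi-square limits at n=130: 0.490 × 0.891 = 0.436 and 0.490 × 1.139 = 0.558. The upper limit is impossible.
- The 1.5 ratio: 0.490 × 1.5 = 0.735, also impossible.
- Wilson interval for a 60% rate at n=130: 51.4% to 68.0%, implying an SD of only 0.466 to 0.500.
- Wilson interval for the control-arm rate: 47.9% to 71.0% at n=65, and 39.6% to 77.5% at n=22.

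The 60% applies to women. At an illustrative rate of 20%, SD = 0.40 and the chi-square upper limit, 0.456, is possible. It still adds nothing to the rate.

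**The case against.** The strongest reply is that the sentence at issue is an illustration: it sits in parentheses, opens as an example, is conditional and names no outcome. Nothing in this pilot's conduct or analysis depends on it, and a future application would need its own justification. That stands, and it limits how much weight the point can bear.

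A reader might infer that the SAP's SD of 15 is itself too low for count outcomes. The figures do not support that. Applied literally at n=130, 1.5 × SD falls short in under 1% of pilots in all three tabled scenarios. It fails more often than 2.5% only under heavier skew, or at n=53 with strong skew, and the documents give no data on skew.

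A reader might also take it as stated that the outcomes are skewed counts and that SA is yes/no. Neither is stated. The at-least-one wording describes a cited base rate, not this trial's endpoint, and the earlier trial used severity and frequency. If SA is scored that way here, the 0.50 ceiling does not apply.

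What the reply leaves untouched is that the protection in 15 comes from a labelling error, not from an allowance for skew. Correcting the label alone takes the multiplier from 1.5 to 1.24 at n=53, or 1.14 at 130 completers, and the shortfall in step 3 then appears.

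**Conclusion.** The point holds as a conditional one about method. Without assumptions about the outcomes: 53 with 7 to 15 is a normal-theory variance interval labelled as an SD interval, and the SD limits are 8.4 to 12.4 (8.9 to 11.4 at 130 completers). On the assumption of negative binomial counts with moderate to strong skew: the correctly computed limit lies below the true SD in about 10 to 24% of pilots of 130, against 2.5% nominal. On the assumption that SA is scored any versus none: an SD limit is redundant at any rate, and impossible at the SAP's 60%.

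The simulations treat the 130 completers as one homogeneous sample; the true shortfall depends on distributions that the documents do not give. The correction is worth making because this is the quantity that the pilot was sized to deliver. It does not bear on the pilot's validity or on participants.

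**What to change.** In the SAP, Sample Size and Analyses:

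1. Label the example interval as one for a variance, or replace its limits with 8.4 to 12.4, and say which outcome it refers to.
2. State the scale of each outcome: count, frequency, severity score or any versus none.
3. For counts, frequencies and scores, take the planning limit from a kurtosis-adjusted (Bonett) or bootstrap 95% interval on the pooled within-group SD. Do not compute it separately in arm-by-risk-group cells of about 22, where it would be very unstable.
4. If SA is any versus none, drop the SD. Report the 3-month control-arm rate with its Wilson 95% interval (about 48% to 71% at n=65 if the rate is 60%) and plan from those limits.

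The cost is a few sentences and a different interval routine, with no change to recruitment or data collection. The price is a less favourable interval: the Bonett interval was about 1.5 to 2.2 times as wide as the chi-square one in the tabled scenarios. It also does not fully reach nominal coverage, since its upper limit was still exceeded in 6 to 8% of pilots.
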